3.3 Statistical analysis

Metrological data is expressed as mean \pm standard deviation (SD). The baseline variables are compared by independent t-test for measurement data and by χ^2 test for count data between Group M and Group N. The means of Kt/V are calculated for every patient and they are compared between two groups. Whether the AVF could be mature or not, predict factors are detected by Logistic Regression among these parameters on basement. The differences of the parameters between two groups are compared using General Linear Model Repeated Measures (GLM-RM) for continuous variables during following up. The results of GLM-RM can also identify the parameters' changes along with the timeline. The outcome events were compared between intervention group and control group. $P < 0.05$ is considered to indicate a significant difference. All of the analyses are performed using SPSS software (version 13.0 for Windows; SPSS Inc., Chicago, IL, USA).

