At present, maintenance hemodialysis (MHD), globally, is the most common method of renal replacement treatment (RRT) for patients with end-stage renal diseases (ESRD). As a core technical problem of MHD, functional vascular access is the base of proceeding the treatment. It is well accepted as an important acknowledgment that native arterovenous fistulas (AVF) should be the first choice for vascular access. The construction of a functional AVF can be challenging, and high initial failure rates have been reported in many publications. Estimates of non-maturation rates vary from 10% to 33% in AVF. However, there are no well-established criteria that define fistula maturation. According to the vascular access guidelines of the National Kidney Foundation Kidney Disease Outcomes Quality Initiative (NKF-KDOQI), mature permanent access has a flow of approximately 600 mL/min and a minimum diameter of 0.6 cm and is less than 0.6 cm below the surface of the skin. The arterialized veins of AVF should have a flow of more than 500 mL/min and a diameter larger than 0.5 cm, and be less than 0.6 cm deep according to the Chinese Expert Consensus of Vascular Accesses for Hemodialysis. Even when the Chinese standard was considered, there were 31.2% (101/324 patients) non-mature AVF in stable long-term (more than six months) MHD patients in eight hemodialysis centers in our previous cross-sectional study. However, their AVF could support enough flow to get an effective urine clearance ratio ($Kt/V > 1.2$) during every hemodialysis session, which should be regarded as the functional accesses in our opinion. What are the differences between functional but non-mature AVF and function-and-maturation AVF? To the best of our knowledge, rarely there are reports on the functional access. Thus, in order to identify the characteristics of functional access in newly set-up AVF in MHD patients, we designed the prospective cohort study.

2. Aim of the study

To describe the ultrasound characteristics of newly set-up arteriovenous fistulas (AVF), also to identify predictors for maturation of AVF in the forearm.

To test the benefits of the ultrasound following-up protocol on AVF in MHD patients.

3. Methods

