During following up, vascular ultrasound examinations for assessment of AVF are proceed at the end of two weeks (t1), two months (t2), three months (t3), and six months after operation (t6), regularly. When patients are detected by ultrasound, they lie down and expose the arm completely. The distal segment of brachial artery (a1), proximal segment of radial artery (a2) and ulnar artery (a3), distal segment of radial artery (a4) and ulnar artery (a5), cephalic vein draining segment nearly 0.5 cm far from the anastomosis (a6), and cephalic vein downstream segment nearly 0.5cm far from a6 (a7) should be examined by linear transducer with higher-frequency (3-12 MHz) using Philips Ultrasound equipment (HD11XE, CX50, IU22, Philips Ultrasound, USA.)

(Figure 1) .The sonographic evaluation parameters including lumen diameter (D), resistance index (RI), blood flow volume (BFV) of every vascular segment above will be measured and recorded. These evaluations are performed by two experienced radiologists in ultrasound, respectively, and all results would be averaged. The procedure of ultrasound examination follows the suggestion of America Institute of Ultrasound in Medicine (AIUM).

[figure not shown]

Figure 1 Ultrasound examination sites of arteriovenous fistula in forearm

The sign of a1 is the distal segment of brachial artery, a2 is the proximal segment of radial artery, a3 is the proximal segment of ulnar artery, a4 is the distal segment of radial artery, a5 is the ulnar artery, a6 is the cephalic vein draining segment nearly 5 cm far from the anastomosis, and a7 is the cephalic vein downstream segment more than 5 cm far from a6.

Physical examination would be performed by experienced nurses to decide if the AVF could be punctured for MHD at the end of third month after operation. The urine clearance index of Kt/V is calculated once per month by simple single pool module, which using pre- and post-dialysis blood urine concentrations in one midweek hemodialysis session when the AVF punctuation begin. The first testing of Kt/V was performed after three times successful cannulations of the new AVF during hemodialysis treatments. If there were several values of Kt/V , mean value of Kt/V would be calculated and been used in statistic analysis.

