All AVF give a dialysis session of mean $Kt/V > 1.2$ would be defined as a functional access. If the $Kt/V \leq 1.2$ and uncapable cannulation repeatedly, the AVF is certified as dysfunctional. The enrolled patients with functional AVF will be divided into Maturation group (Group M) and Non-maturation group (Group N). Mature AVF is defined as both $BFV(t3) > 500 \text{ ml/mL}$ and $D(t3) > 0.5 \text{ cm}$, otherwise, the AVF would be stated as non-maturation. Because the distance from skin to AVF veins in forearm is seldom larger than 0.6 cm in Chinese MHD patients, we ignored this parameter in this study.

All adverse events of dialysis accesses will be recorded in enrolled patients, including secondary AVF operation, thrombosis of AVF, stenosis, puncture failure, bleeding at puncture point after dialysis, and so on.

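### The only predictor analysis for Aim 1 models one pass/fail maturation label, discarding recorded flow and diameter values and pooling two kinds of failure; continuous models should be added beside it.

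*Combined protocol and SAP*

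**What the plan says.** Section 2 states the aim, among others, "also to identify predictors for maturation of AVF in the forearm". Section 3.2 provides for detailed ultrasound at each visit: diameter, resistance index and "blood flow volume (BFV) of every vascular segment above will be measured and recorded", with two radiologists' readings averaged. These are continuous measurements.

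Section 3.2 then reduces the t3 values to one label. "Mature AVF is defined as both" BFV(t3) above 500 and D(t3) above 0.5 cm; "otherwise, the AVF would be stated as non-maturation". The non-mature class therefore holds AVFs that fail on flow only, on diameter only, or on both.

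Section 3.3 uses this label as the outcome of the sole predictor model: "Whether the AVF could be mature or not, predict factors are detected by Logistic Regression among these parameters on basement". The t-tests, chi-squared tests and repeated-measures models compare Group M with Group N, so the same label is their grouping factor. None of them relates a baseline factor to t3 flow or t3 diameter.

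**The concern.** Under the label, an AVF with a flow of 490 counts the same as one at 100, and, if diameter passes, 510 counts the same as 1500. A baseline vessel feature that shifts flow or diameter is seen by the model only through the AVFs it carries across a cut.

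The two-part rule adds a second problem. A feature that affects flow but not diameter is diluted, because some AVFs are non-mature on diameter alone. Even if it is detected, the plan cannot say which measure it acts on.

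What is at stake is the power of a one-centre cohort with no stated sample size to find predictors, and how those predictors can be interpreted. The introductory text also says that maturation criteria are not settled and cites two pairs of cuts (about 600 mL/min with 0.6 cm; 500 mL/min with 0.5 cm). Predictor results that exist only for one pair cannot be carried over to the other.

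**Working it through.** **Figures in the documents.** No sample size, power or effect size is given, so there is no design figure to reproduce. The documents give two non-maturation rates: "Estimates of non-maturation rates vary from 10% to 33% in AVF", and "there were 31.2% (101/324 patients) non-mature AVF in stable long-term (more than six months) MHD patients". Check: 101/324 = 0.3117, which agrees with 31.2%.

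**Benchmark: one normal outcome, one cut.** For a weak predictor and non-mature share q, the efficiency of the yes/no outcome relative to the continuous one is φ(z)²/[q(1−q)], where z is the q-quantile of the standard normal.

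- q = 0.10: 0.342, so a continuous analysis is worth 1/0.342 = 2.92 times the patients.
- q = 0.312: 0.3538²/(0.312 × 0.688) = 0.583; inverse 1.72.
- q = 0.33: 0.593; inverse 1.69.

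This does not match the plan, which cuts two outcomes and requires both to pass.

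**Two cuts.** Assumptions: flow (on a suitable scale) and diameter are bivariate normal with correlation ρ, the standardised cut c is the same for both, and the predictor is weak and linear. Choose c so that P(both > c) = 1 − q. The sensitivity of P(mature) to a shift in one measure is

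g = φ(c) · Φ(−c√[(1−ρ)/(1+ρ)]).

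- Predictor acts on one measure only: efficiency against a regression on that measure is E₁ = g²/[q(1−q)].
- Predictor shifts both equally: efficiency against a regression on either measure is (2g)²/[q(1−q)] = 4E₁.

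At q = 0.312, q(1−q) = 0.2147. For ρ = 0: c = −0.952, φ(c) = 0.2536, Φ(·) = 0.8295, g = 0.2103, so E₁ = 0.0442/0.2147 = 0.206 and 4E₁ = 0.824. In the same way:

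| ρ | c | g | Loss, one measure only (1 − E₁) | Loss, both equally (1 − 4E₁) | Non-mature: flow only / diameter only / both |
|---|---|---|---|---|---|
| 0 | −0.952 | 0.2103 | 79% | 18% | 45 / 45 / 9% |
| 0.3 | −0.896 | 0.1989 | 82% | 26% | 41 / 41 / 19% |
| 0.5 | −0.844 | 0.1920 | 83% | 31% | 36 / 36 / 28% |
| 0.9 | −0.660 | 0.1797 | 85% | 40% | 18 / 18 / 63% |

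**Sensitivity to the rate.** The same formulas for ρ from 0 to 0.9 give:

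- q = 0.33: losses of 16% to 39% (both equally) and 79% to 85% (one only).
- q = 0.10: losses of 56% to 65% (both equally) and 89% to 91% (one only).

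**Sensitivity to unequal cuts.** Let the flow cut be more binding by 0.7 SD, at q = 0.312.

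- ρ = 0.7: the loss is 57% for a flow-only predictor, 98% for a diameter-only predictor and 38% for an equal shift.
- ρ = 0.9: the figures are 47%, about 100% and 41%.

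**Price of multiplicity.** Testing two outcomes at 0.025 each instead of 0.05, at 80% power, inflates N by [(2.241 + 0.842)/(1.960 + 0.842)]² = 9.505/7.849 = 1.21. At q = 0.312 with equal cuts, one continuous model taken alone is then worth the following, relative to the label at 0.05:

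- Equal shift, ρ = 0: (1/0.824)/1.21 = 1.00, so the gain is used up.
- Equal shift, ρ = 0.9: (1/0.602)/1.21 = 1.37.
- One measure only, ρ = 0: (1/0.206)/1.21 = 4.0.

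**The case against.** The strongest reply is that crossing the threshold is the question. Aim 1 concerns maturation, the protocol takes maturation from a consensus rule on flow and diameter, and treating 510 like 1500 is what such a rule means. A predictor of mean flow need not predict maturation. This stands: the binary model targets a legitimate estimand, and Aim 1 should not be moved off it. It does not answer the point that nothing else is planned.

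A reader might infer from the one-cut benchmark that the label always costs 40% or more. The documents do not support that. The rule has two cuts, and against a single continuous model the loss can be 18% or less when a predictor shifts both measures. It can also be far larger.

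The rates are borrowed as well. The 31.2% comes from stable long-term patients, the 10% to 33% range is from publications in a field that the protocol says lacks agreed criteria, and Groups M and N contain functional AVFs only. The non-mature share in this cohort is unknown.

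A reader might also infer that many AVFs near the cuts will change class through measurement noise. Some may, but no measurement error is given and two readings are averaged, so the extent cannot be judged.

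Finally, two added outcomes raise multiplicity, and section 3.2 does not say which vessel segment supplies BFV(t3) and D(t3). Both objections hold and have to be dealt with in the fix.

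**Conclusion.** The structural point holds on the text. One logistic regression on a two-criterion label is the only predictor analysis, and it discards recorded information and mixes failure types.

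The size is conditional. With approximate normality, a weak linear effect, equal cuts and 31.2% non-mature, the loss against a single continuous model is about 18% to 40% if a predictor shifts flow and diameter equally (ρ from 0 to 0.9), and about 79% to 85% if it acts on one measure only. Unequal cuts or another rate move these figures, as the sensitivity results show, and neither range is a floor. Without a sample size or effect size, they cannot be turned into a power figure for this study.

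The plan is not invalid on this account. The change is an inexpensive improvement to Aim 1.

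**What to change.** 1. Keep the logistic model for maturation as the analysis of the protocol's endpoint.
2. Add prespecified regressions of log BFV(t3) and of D(t3) on the same baseline predictors. State which vessel segment defines the label and use the same segment here.
3. If occluded AVFs are included, use a proportional-odds model with them at the lowest rank, since log flow is undefined at zero.
4. Tabulate non-mature AVFs by failed criterion: flow only, diameter only, both.
5. State the multiplicity choice in advance: either label the continuous models supportive, or adjust alpha. Adjusting gives back part of the gain, and nearly all of it in the least favourable case shown.

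The cost is analysis-plan wording, two models and one table on data already collected. No visit or measurement changes. The downside is two additional outcomes to report and reconcile with the logistic result.

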3.1 Patients

Patients beginning MHD treatment in Peking University International Hospital from July 2016 will be screened. If patients fit to the selection criteria, they might be enrolled into the present study. Enrolled patients were divided into intervention group and control group.

3.1.1 Entry criteria:

- ① Regular hemodialysis patients (4 hours per session and three times a week).
- ② Planning to construct a new radiocephalic AVF in forearm.
- ③ 18-70 years old.

3.1.2 Exclusion criteria:

- ① Predicted duration of MHD less than six months, such as transferring to peritoneal dialysis, planning to kidney transplantation, or short life expectancy, etc.
- ② Have the following complications: malignant tumors, active rheumatism, malnutrition and cachexia.
- ④ Acute renal dysfunction.
- ④ Having done any blood vessel operations on the same side of the arms that planned to create an AVF. But it was not been care in the present study whether there were vascular accesses or not in the contralateral arm.
- ⑤ Not accepted AVF personally.
- ⑥ Other kinds of vascular accesses, such as brachiocephalic AVF, upper limb AVF, graft accesses, and so on.

3.2 Detection and following up of the intervention group:

The basic information of the patients, including gender, age, dialysis length, hemodialysis access, and primary causes of renal failure, will be collected. The baseline data will be recorded, including height, weight, BMI, and blood pressure (BP). Ultrasonography detection on the forearm blood vessels would be conducted before the surgery of AVF creation (time 0, t0). The operations will be conducted by a certain nephrologist with more than ten years experience of doing AVF surgeries. Until the patients finish the AVF operation, they would be followed up at least six months.

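### Predictors of maturation are sought among about 24–30 baseline parameters at P<0.05, with no multiplicity control, shrinkage or validation

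*Combined protocol and SAP*

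**What the plan says.** Finding what predicts maturation is one half of the first aim in Section 2. The method is one sentence in Section 3.3: "predict factors are detected by Logistic Regression among these parameters on basement". The same section says that P<0.05 "is considered to indicate a significant difference", without distinguishing between analyses. It gives no candidate list, no rule for entering or removing variables, no cap on their number, no multiplicity rule, no shrinkage and no validation.

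The pool has to be read from Section 3.2. On demographic and clinical items: "The basic information of the patients, including gender, age, dialysis length, hemodialysis access, and primary causes of renal failure, will be collected". On physical items: "The baseline data will be recorded, including height, weight, BMI, and blood pressure (BP". On imaging before surgery: "Ultrasonography detection on the forearm blood vessels would be conducted before the surgery of AVF creation (time 0, t0". The segments scanned at t0 are not listed. The only segment list, a1 to a7, belongs to the description of the follow-up scans, where "lumen diameter (D), resistance index (RI), blood flow volume (BFV) of every vascular segment above will be measured and recorded".

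No sample size, expected number of non-mature fistulas or end of recruitment is stated. The background before Section 2 supplies the only rates. From the literature: "Estimates of non-maturation rates vary from 10% to 33% in AVF". From the sponsor's earlier study: "31.2% (101/324 patients) non-mature AVF in stable long-term (more than six months) MHD patients in eight hemodialysis centers".

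**The concern.** Detecting predictors among everything measured at baseline is an open search. Each extra candidate tested at 0.05 adds a chance of a false finding, and nothing in Section 3.3 offsets this. When there are also few non-mature fistulas per candidate, the coefficients and P-values of a large logistic model become unreliable as well. The pool is partly redundant too: BMI is calculated from height and weight, and diameter, resistance index and flow in neighbouring segments can be expected to be correlated.

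A reader of the results could not tell a real predictor of maturation from a chance one, and this is a stated aim of the study.

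**Working it through.** The plan gives no design figure for this analysis to reproduce. Its one relevant proportion checks: 101/324 = 0.3117, or 31.2%.

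**Candidate count (Section 3.2).**
- Demographic and clinical: 5. Physical: 4. Together 9.
- Ultrasound: 3 measures × 7 segments = 21, giving 21 + 9 = 30.
- Segments a6 and a7 are located by distance from an anastomosis that does not exist at t0. Without them: 3 × 5 = 15, giving 15 + 9 = 24.
- Splitting blood pressure into systolic and diastolic would make 30 into 31. Coding cause of renal failure by category would add more.

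**False findings if no candidate is real, independent tests.** Expected number = 0.05k; chance of at least one = 1 − 0.95^k.
- k = 24: 1.2 expected; 1 − 0.95^24 = 70.8%.
- k = 30: 1.5 expected; 1 − 0.95^30 = 78.5%.
- k = 3, for comparison: 1 − 0.95^3 = 14.3%.

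**Simulation, no real predictors.** N is assumed and about 31% of fistulas are non-mature. For the full model, 21 candidates are correlated at 0.3 and 9 are independent. For forward selection, all 30 are independent. Cells give the share of datasets with at least one false predictor at P<0.05.

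| N | Full model, 30 | Full model, 24 | Forward selection, 30 |
|---|---|---|---|
| 100 | 89–91% | 80% | 80% |
| 200 | 85% | 76% | 79% |
| 324 | 80–84% | 73% | 77% |
| about 960 | 76% | not tabulated | 78% |

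With 300–500 datasets per cell the simulation error is about 2 percentage points, e.g. √(0.8 × 0.2/400) = 0.02. In the 30-candidate full model the mean number of false predictors falls from 3.2 at N = 100 to 1.56 at N = 962. A univariable screen gives about 70% with 30 candidates and 64–68% with 24, whatever the N. A three-variable pre-specified list gave 10–16%.

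**Simulation, some real predictors.** Forward selection among 30 independent candidates, assumed odds ratio 1.8 per SD, 200 datasets per N. False share = mean false/(mean false + mean true).

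| N | 3 real | 5 real |
|---|---|---|
| 100 | 1.65/3.62 = 46% | 1.57/4.72 = 33% |
| 200 | 1.47/4.22 = 35% | 1.65/6.21 = 27% |
| 324 | 1.61/4.61 = 35% | 1.32/6.25 = 21% |
| 960 | 1.25/4.25 = 29% | 1.39/6.39 = 22% |

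**Non-mature fistulas per candidate.** Earlier eight-centre sample: 101/30 = 3.4; 101/24 = 4.2. At 31.2% and N = 100: 31.2/30 = 1.0; 31.2/24 = 1.3. Ten per candidate is a rule of thumb and does not come from the documents. It would need 300/0.312 = 962 patients for 30 candidates or 240/0.312 = 770 for 24. At 10% non-maturation these become 3,000 and 2,400. At five per candidate, 30 candidates need 150/0.33 = 455 to 150/0.10 = 1,500. Groups M and N contain only functional fistulas, so these N are fewer than all enrolled.

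**The case against.** Four stronger readings are tempting, and the documents do not carry them.

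- *That a one-centre cohort cannot support this model.* Section 3.1 opens screening in July 2016 with no end and no target. The earlier sample was a cross-section of long-term patients, so its size puts no bound on this cohort. Adequacy cannot be judged either way.
- *That most of the predictors found will be false.* This holds only if few or no candidates are real. With three to five moderate true predictors, the false share stayed below half at every N examined.
- *That a larger cohort would cure it.* With pure-noise candidates, at least one false predictor still appears in about 76–78% of datasets at about 960 patients. The main cause is multiplicity; small numbers aggravate it.
- *That the plan will publish an inflated AUC.* Section 3.3 promises no AUC, ROC curve or risk score. If one were reported, optimism would matter: with three real predictors and N = 100, the apparent AUC averaged 0.80, against 0.66 in new data.

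It is also fair to say that the candidate count is inferred, that Section 3.3 does not say all candidates enter one model, and that the simulated correlations and effect sizes are assumptions. These points widen the range without removing the problem: it remains with 24 candidates, and under full-model, forward and univariable approaches alike.

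**Conclusion.** The point holds in a limited form. Followed as written, Section 3.3 searches about 24–30 baseline parameters at P<0.05 with nothing to contain chance findings. If none were real, roughly 70–90% of studies of 100 to about 960 patients would name at least one false predictor, or slightly fewer (64–68%) under a univariable screen of 24. With three to five true predictors of odds ratio 1.8 per SD, about 20–46% of the variables selected would be false. Every N is an assumption because the plan gives none, as are the effect sizes and correlations.

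The plan should change, because the stated rule gives unreliable answers to an aim of the study at any of the sizes examined. The documents do not establish that the cohort will be too small or that the predictors will be mostly spurious.

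**What to change.** Before any three-month (t3) data are seen, replace the open search in Section 3.3 by one of two methods.

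- **(a) A short pre-specified list.** The sponsor chooses the candidates and sizes the list to the expected smaller outcome group, at about one parameter per 10 fistulas (a rule of thumb). At 31.2% non-mature that is about 3 parameters for 100 patients, 6 for 200 and 10 for 324. At 10% it is 1, 2 and 3.
- **(b) One penalised logistic model** (ridge or lasso) that does not enter height, weight and BMI together. It has not been shown here that variable selection by this route would be stable with only about 31 non-mature fistulas, so (a) is the safer choice at that size.

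In either case:
- State which segments are measured at t0.
- Do no univariable or stepwise selection at P<0.05.
- Label predictors outside the pre-specified list as exploratory.
- If any model performance is reported, give bootstrap optimism-corrected values.

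The cost is a rewritten paragraph and some extra analysis, possibly outside SPSS 13. Fewer variables could be called predictors. Even a three-variable list tested at 0.05 keeps a chance of about 14% of at least one false finding.

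### Groups M and N are defined by D and BFV at t3, and the same D and BFV series, t3 included, are then tested between M and N, so group-by-time rejects too often unless within-patient correlation is near 1

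*Combined protocol and SAP*

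**What the plan says.** - **Grouping (section 3.2).** "The enrolled patients with functional AVF will be divided into Maturation group (Group M) and Non-maturation group (Group N"). The rule begins "Mature AVF is defined as both $BFV(t3) > 500" and adds a t3 diameter above 0.5 cm; a fistula that misses either criterion goes to Group N. The rule does not say which of the segments a1 to a7 it refers to.
- **Schedule (section 3.2).** Follow-up scans take place at "two weeks (t1), two months (t2), three months (t3), and six months after operation (t6"), so the classification visit is one of the four.
- **Measurements (section 3.2).** At each scan, "lumen diameter (D), resistance index (RI), blood flow volume (BFV) of every vascular segment above will be measured and recorded". Three parameters at seven segments make 21 series.
- **Test (section 3.3).** "The differences of the parameters between two groups are compared using General Linear Model Repeated Measures (GLM-RM) for continuous variables during following up", with significance at P < 0.05. Changes over time are read from the same model.

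The two groups here are M and N. They are the only pair named in section 3.3 before that sentence. Intervention versus control comes later and only for outcome events, and the scan schedule is described only for the intervention group.

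**The concern.** The outcome of the comparison is also the rule that forms the groups. For D and BFV at the defining segment, M and N must differ at t3. At the other visits the same patients were not selected on that visit's value, so their gap is smaller. The result is a gap that peaks at t3, which GLM-RM reports as a group-by-time interaction.

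The background section poses the question "What are the differences between functional but non-mature AVF and function-and-maturation AVF", and D and BFV are the curves a reader would look at first. A significant interaction would be read as mature fistulas following a different course, yet cutting one homogeneous population at t3 gives the same picture. The group main effect also includes t3. It mostly reflects real persistence of patient differences once within-patient correlation is 0.6 or more, but it still shows association with t3 status and is not an independent finding.

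**Working it through.** The plan gives no figure to reproduce here.

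**Inputs from the documents.** Grouping rule, visits at 0.5, 2, 3 and 6 months, and alpha 0.05, as above. Non-mature share 31.2% (101/324 = 0.312), which the background reports for stable long-term patients. Because new fistulas may differ, the background's literature range is also used: "Estimates of non-maturation rates vary from 10% to 33% in AVF".

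**Assumptions, not in the documents.** n = 40 or 80 functional fistulas; within-patient correlation rho; same-visit D-BFV correlation 0.5. Section 3.2 says "These evaluations are performed by two experienced radiologists in ultrasound, respectively, and all results would be averaged", which lowers scan noise and is a reason to look at the higher correlations, but it fixes no value.

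**Reference situation.** One homogeneous population: D and BFV are standard normal at every visit, with the same mean course for everyone. Group M has both t3 values above cut-offs set so that 31.2% fail the joint rule.

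**Step 1: the gap.** With constant spread, gap at visit j = corr(j, t3) × gap at t3. The simulated t3 gap in D is 1.34 SD. Elsewhere it is 0.6 × 1.34 = 0.80 SD at rho = 0.6, and 0.9 × 1.34 = 1.21 SD at rho = 0.9.

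**Step 2: approximate size by formula, equal correlation between visits.** With t3 gap δ, the gaps deviate from their mean by 0.75(1 − rho)δ at t3 and by −0.25(1 − rho)δ at the other three visits. The sum of squares is (0.5625 + 3 × 0.0625)(1 − rho)²δ² = 0.75(1 − rho)²δ². Dividing by the within-patient variance (1 − rho) and multiplying by n_M·n_N/n gives the noncentrality

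λ = n × 0.312 × 0.688 × 0.75 × δ² × (1 − rho).

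For n = 40, rho = 0.6: 8.59 × 0.75 × 1.796 × 0.4 = 4.63. The F test on 3 and 114 degrees of freedom then rejects in about 40%. For n = 80, λ = 9.25 and the rate is about 72%.

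**Step 3: simulation (20,000 trials per cell), group-by-time for D, nominal 5%.**

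| rho | n = 40 simulated | n = 40 formula | n = 80 simulated | n = 80 formula |
|---|---|---|---|---|
| 0.3 | 68% | 64% | 96% | 93% |
| 0.6 | 41% | 40% | 74% | 72% |
| 0.8 | 22% | 21% | 42% | 40% |
| 0.9 | 13% | 12% | 21% | 21% |

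Random grouping (n = 60, rho = 0.7) gives 3.9 to 4.3%, so the test itself holds its level. At least one of D and BFV rejects in 59% / 89% at rho = 0.6 and 21% / 35% at 0.9 (n = 40 / 80); the comparison there is about 9% for two tests, not 5%.

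**Step 4: how near 1 is near enough.** This depends on n. With Greenhouse-Geisser correction, rho = 0.95 gives 5.5% at n = 20, 6.4% at n = 30 and 26% at n = 200. At n = 200, rho = 0.99 still gives 8.9%. At rho = 0.999 the rate is 4.5 to 5.2% for every n tried (20 to 200).

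**Step 5: sensitivity at rho = 0.6 (n = 40; n = 80).**
- Non-mature share 10 / 20 / 33%: 25 / 34 / 41%; 46 / 64 / 75%.
- D-BFV correlation 0 to 0.9: 23 to 56%; 44 to 90%.
- One criterion failing three times as often as the other: 25 to 54%; 49 to 88%.

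The same checks at rho = 0.9 give 9 to 16% and 13 to 28%.

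**Step 6: does leaving out t3 cure it?** With equal correlation and constant spread, yes for group-by-time (4.5 to 4.8% at n = 60). Otherwise no:

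| Setting | With t3 (n = 40 / 80) | Without t3 (n = 40 / 80) |
|---|---|---|
| Correlation 0.6 per month apart | 65% / 95% | 16% / 32% |
| Correlation 0.9 per month apart | 19% / 40% | 9% / 14% |
| SD growing 0.7, 0.9, 1, 1.1; rho 0.6 | 63% / 95% | 12% / 25% |
| SD growing 0.7, 0.9, 1, 1.1; rho 0.9 | 84% / 99% | 71% / 95% |

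In the last row most of the signal is real fanning out. What remains without t3 is a true difference between groups defined at t3, not an independent finding.

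**Step 7: group main effect (equal correlation).** At rho = 0.6 it rejects in 95% with t3 and 84% without at n = 40, and in 100% and 99% at n = 80. At rho = 0.3 the figures are 81% and 36%, and 98% and 63%.

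**The case against.** - **Section 3.3 never names group-by-time.** It can be read as a group effect and a time effect only. But the interaction is standard GLM-RM output and the natural way to read group differences during follow-up, and nothing in the plan sets it aside. The group effect is also tied to the grouping rule.
- **Rejection is not strictly a type I error.** M and N differ at t3 by definition, so equal profiles is a false null whenever correlation is below 1. This stands as a point of language. The excess over 5% is measured against one homogeneous population with a common course, which is the comparison a reader would have in mind.
- **The size rests on assumptions.** True: n and both correlations are assumed, the main runs hold mean and SD constant in a newly made fistula, and selection on Kt/V > 1.2 is not modelled. In a small study with high correlation the excess almost disappears.
- **The reach is small.** True: at most two of 21 series are directly affected, and the M-versus-N question appears in the background rather than in the listed aims.
- **Removing P values goes too far,** since t1 and t2 precede classification and differences there are a valid association with later maturity. The proposed wording keeps those differences and labels them as association. It withholds only the P values for t3, group and group-by-time.

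**Conclusion.** The concern holds. Followed as written, the plan yields circular P values for D and BFV at the maturity-defining segment. Under a homogeneous population with 31.2% non-mature, D-BFV correlation 0.5 and equal correlation between visits, group-by-time for D rejects in 41% / 74% at within-patient correlation 0.6 and 13% / 21% at 0.9 (n = 40 / 80), against 5%. These rates illustrate the problem rather than predict it, because n and the correlations are not in the documents. The direction does not depend on them unless correlation is near 1, and how near depends on n.

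RI and the other segments are affected only through their correlation with the defining values. The baseline tests, the logistic regression, the overall time effect over all functional fistulas together and the intervention-control comparison are untouched. The change should be made; it does not call the rest of the plan into question.

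**What to change.** 1. In section 3.2, name the segment whose D and BFV define maturity.
2. Add to section 3.3:

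> For D and BFV at [named segment], which define Groups M and N at t3, mean, SD and number scanned will be shown by group at t1, t2, t3 and t6, without P values for t3, group or group-by-time. Differences at t1, t2 and t6 will be reported as association with maturity at t3.

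3. Keep the GLM-RM group and group-by-time tests for parameters that do not define the groups, such as RI, and note their correlation with D and BFV.
4. Test the overall time effect for D and BFV over all functional fistulas together, without the M/N factor.
5. Leave the baseline tests, logistic regression and intervention-control comparison as they are.

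Dropping t3 from the model is not a sufficient substitute. The cost is wording only, with no new data or software. What is lost is a formal between-group test of course for the two defining parameters, a test that cannot separate a different course from the grouping rule.
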